14.1.1. Data management procedures

Database lock will be agreed by data manager, principal and sub investigator, and study project leader in a clean file meeting before any data analysis. Database lock will be done at the end of the study, when all six month data is available.

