7. Justification for the design of the clinical study

[figure not shown]Signing informed consent		X					X		
BC-thresholds			X						
Interview about SP				X		X	X	X	(X)
Fitting of sound processor			X						
BC In-situ			X						
Feedback margin measurement			X						
Fine tuning			(X)		X	(X)	X	(X)	(X)
			(X)		(X)	(X)	(X)		(X)
Skull simulator			X		X	(X)	X		(X)
Magnet retention force			X			X	X		(X)
Sound field threshold and speech			x BCI x Fusion			x Fusion	x Fusion x Unaided	X Fusion new setting	
AE				X	X	X	X	X	X
Questionnaires			x BCI			x Fusion	x Fusion	X Fusion new	
Photo			X With SP			x Without SP	x Without SP		(X)

Table 1 Content of Fusion sound processor study

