- Magnet force measurement and skin evaluation
- Sound field thresholds and speech intelligibility measurements on Fusion SP
- Fine tuning to apply additional setting
- Skull simulator on Fusion SP after fine tuning
- Adverse events during the visit.
- [REDACTED]
- Go through information about adding on an extra visit
- Signing informed consent for adding an extra visit

Fifth visit, seven months

- Adverse events during the test period
- Hand in questionnaires
- Sound field thresholds and speech intelligibility measurements on Fusion SP
- [REDACTED]
- If finetuning: Skullsimulator simulator on Fusion SP after fine tuning

On the fourth visit the magnet force measurements and pictures of the skin under the SP will be repeated. Sound field thresholds and speech intelligibility measurements will be conducted, this time for the Fusion SP and unaided. There is also a possibility for extra fine tuning if needed. In the beginning of the visit adverse events during the test period will be noted.

Unscheduled visits

If any problems arise under the trial, the subjects are advised to contact the sub-investigator. The sub-investigator will evaluate and confer with the investigator if needed. If the problems are SP related (eg. need for fine tuning, loss of SP or malfunctioning SP) appointment with the sub-investigator or if of medical character (eg. skin problem or pain the area under the SP) refer to investigator who will schedule an extra visit.

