10.5. Subject population

All BCI subjects that are included in and have worn the BCI sound processor for one year in the Osseofon study will be offered to participate in this study according to the inclusion criteria below. At the time of enrolment, 13 subjects fit this criteria making up the eligible population for this study. We expect between 6-10 of the subjects offered to participate will accept and be enrolled. The current Osseofon study have no drop outs [17] and we therefore expect all the subjects to fulfil the study and that there is no drop outs during the course of the study. The total time a patient will be enrolled in this study is six months.

Inclusion criteria

- Subjects implanted with the BBC implant
- 
- 
- Active user of the BCI SP

Exclusion criteria

- Inability to participate in follow-ups
- Unsuitable as judged by the principle investigator or the sub-investigator

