13.2. The patient's medical record

The subjects's participation in the clinical investigation will be documented in the patient's medical record along with test subject code, title of the investigation and investigation code. This will be done

by the investigator at the first visit. It will also be documented that the patient has been informed about the study and that the patient has signed the informed consent form. The date of inclusion into the study will be recorded together with the study code. When leaving the study that date will be recorded. Note that if AEs warrants follow-up the date that the last activity to follow the AE up is the last date in the study and not the last visit date. The last date of AE follow-up may have the status ongoing, not recovered or unknown. Ongoing will be used only when a status quo have been reached. Unknown may be used when the subject has been lost to follow-up.

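### Could the six-month lock condition shut the month-7 visit out of the locked database?

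*Combined protocol and SAP*

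**What the plan says.** The time points sit in five places in the protocol.

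- **Synopsis:** the study period is 7 months.
- **Section 10.3:** the outline ends with "Fifth visit, seven months". That visit collects adverse events, questionnaires, and sound field and speech measurements on the Fusion processor. Under the fourth visit, at six months, the list includes "Signing informed consent for adding an extra visit" and a fine tuning that applies an additional setting.
- **Table 1:** the sound field and speech row contains the entry "X Fusion new setting". The column headers are lost in the public text. The column order and the fine tuning at the fourth visit suggest that this entry belongs to the fifth visit.
- **Section 10.5:** "The total time a patient will be enrolled in this study is six months".
- **Section 14.1.1:** "Database lock will be done at the end of the study, when all six month data is available". Lock is agreed by the data manager, the principal and sub-investigators and the study project leader "in a clean file meeting before any data analysis".

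Section 15 places the primary endpoint at 6 months and has the SAP written before database lock. Section 13.2 records when each subject leaves: "When leaving the study that date will be recorded".

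**The concern.** Two sections speak of six months and two of seven. Six-month data are the only data that section 14.1.1 names as a condition for lock, section 10.5 seems to support a six-month end, and no second lock is described. Section 13.2 gives a leaving date for each subject, but the available text does not define an end of study for the whole trial.

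If someone locked as soon as the last six-month record was in, some fifth-visit data could fall outside the locked set. The new-setting thresholds, speech scores and questionnaires appear nowhere else in the schedule, so they could not be recovered from another visit. The fifth visit's record headed "Adverse events during the test period" could also miss the lock. Because section 14.1.1 places lock before analysis, its timing decides which data are analysed.

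**Working it through.** **1. The time points side by side**

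| Source | Time stated | What it describes |
|---|---|---|
| Synopsis | 7 months | study period |
| 10.3, fifth visit | 7 months | last scheduled visit, by extra consent |
| 10.5 | 6 months | enrolment per patient |
| 14.1.1 | end of study, and 6-month data | lock |
| 15 | 6 months | primary endpoint |

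The gap is 7 − 6 = 1 month. It equals the interval between the fourth and fifth visits, so the synopsis counts the added visit and section 10.5 does not.

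**2. The lock sentence, tested against two dates**

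- Lock when the last six-month data arrive, with fifth visits pending: the six-month condition is met. The end-of-study condition is not, because scheduled visits of a 7-month study are outstanding.
- Lock after the last fifth visit: both conditions are met.

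Only the later date satisfies the whole sentence. Naming the six-month data fits a primary endpoint at that time and does not exclude later data.

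**3. The enrolment sentence**

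The fifth visit needs a consent signed at the fourth visit. Six months is therefore correct for the initial consent and for a subject who declines. It is one month short for a subject who accepts. A per-patient duration does not set the date of a trial-level lock.

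**4. How many subjects an early lock would miss**

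The documents give 6 to 10 subjects, but neither the accrual pattern nor the lag from the last six-month data to lock. Suppose visits run on schedule from fitting and everyone consents to the fifth visit. Let L be the lag in months, so that lock comes 6 + L months after the last fitting. A subject fitted d months before the last one has the fifth visit at 7 − d on the same clock. That visit is missed if 7 − d > 6 + L, that is, if d < 1 − L. With evenly spaced fittings (an assumption):

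| Span of fittings (assumed) | Subjects | L = 0 | L = 0.5 | L = 1 |
|---|---|---|---|---|
| 0.99 month | 6 | 6 | 3 | 0 |
| 0.99 month | 10 | 10 | 5 | 0 |
| 3 months | 6 | 2 | 1 | 0 |
| 3 months | 10 | 3 | 2 | 0 |
| 6 months | 6 | 1 | 1 | 0 |
| 6 months | 10 | 2 | 1 | 0 |

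As an example, 6 subjects over 3 months have d = 0, 0.6, 1.2, 1.8, 2.4 and 3.0. With L = 0, two values lie below 1; with L = 0.5, one lies below 0.5.

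These are not upper bounds. If all fittings fell within less than half a month, a half-month lag would still miss everyone. For L of 1 or more, 1 − L is zero or negative and nobody is missed under any accrual pattern. Consent below 100% can only lower the counts. The range is none to all, and it is set by the assumptions.

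**5. The primary test**

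Section 10.5.1 gives a minimum of 6 patients if all improve. The smallest two-sided signed-rank p-value is 2 × (1/2)^n: 0.0625 for n = 5 and 0.03125 for n = 6. At an assumed two-sided 0.05 level the minimum is 6, as stated. It uses six-month data only, so lock timing around month 7 does not affect it.

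**The case for a change.** The strongest case for a change is that the safe reading rests on an end of study that the available text never defines for the trial. Section 10.5 points to month 6, and it is literally wrong for a subject who attends the fifth visit. The pattern looks like a visit added late and not carried through to sections 10.5 and 14.1.1. The text after the fifth-visit list in section 10.3 also describes only the fourth visit. Alignment would take a few words, and one clear end date would also serve the hand-over of adverse events to the parallel Osseofon study in section 21.

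The wording mismatch stands. The harm does not follow from it, for these reasons:

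- An early lock requires reading half of the lock sentence and setting aside the synopsis.
- The missing definition carries little weight. The endpoint sections are absent from the public text and much of section 13 is redacted, so a definition cannot be ruled out.
- Lock needs the agreement of the sub-investigator. Under sections 13.3 and 14 this person holds the appointments and enters the questionnaire data, and so would know that fifth visits were outstanding.
- The SAP, due before lock, can state how the fifth visit is handled.
- Section 21 shows no conflict. Adverse events are reported in both studies, later ones pass to the Osseofon study, and the reporting timelines in section 21.8 do not depend on database lock.

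**Conclusion.** This is a clerical slip with a sensible default. Section 10.5 was not aligned with the optional fifth visit, and section 14.1.1 leaves the month-7 data unnamed while still requiring the study to have ended. Followed as written, the plan locks after the fifth visits and gives sound results, so no change is called for.

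The slip amounts to one month of wording. The number of subjects at risk under an early lock is undetermined, from none to all, and is none with a lag of one month or more. The six-month primary analysis and the sample size are unaffected under any reading.

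The conclusion rests on taking the synopsis duration as covering the fifth visit, which matches its timing exactly. Whether any endpoint uses fifth-visit data cannot be checked in the public text.

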14.2. Confidentiality

At all times throughout the clinical investigation confidentiality will be observed by all parties involved. All data will be secured against unauthorized access.

15. Statistical considerations

To evaluate the differences between the unaided and Fusion SP aided threshold at 6 months (primary end-point) a non-parametric test (Wilcoxon Signed Rank test) will be used. A detailed statistical analysis plan (SAP) will be developed prior to database lock by an independent biostatistician (compare Sec. 13). In general, pairwise differences for continuous variables will be tested with Wilcoxon Signed Rank test and for ordered categorical variables with Sign test. Last value carried forward will be used for potential drop-out subjects. If imputation is used, sensitivity analysis will be performed for the primary outcome, and selected additional outcome variables as defined in the statistical analysis plan.

16. Amendments to the CIP

In case of changes to the clinical trial protocol are needed, an amendment should be made. Substantial amendments should be approved by the competent authorities and ethical committee before incorporated.

17. Deviations from clinical investigation plan

The investigator should not deviate from the clinical investigational plan except if needed to protect the rights, safety and well-being of the subjects. Such cases should be documented and reported to the EC and the Sponsor as soon as possible.

If deviations (other than mentioned above) occur, the Investigator should inform the monitor/clinical study manager and record in the protocol deviation log provided in the study site file. The implications of the deviation must be reviewed and discussed between the Sponsor and the Investigator. If deviations are found during monitoring visits, they should also be documented in the monitoring report and handled as above. This should be done as soon as possible after detection to avoid repetitive deviations. Continuous review of protocol deviations during monitoring visits aim to detect systematic errors and to identify retraining needs at the site. Frequency of monitoring is described in the monitoring plan and should be increased if systemic deviations are identified.

All protocol deviations must be documented stating the reason, date, the action(s) taken, and the impact for the subjects and/or the study.

If serious or repeated deviations occur, the Sponsor has the right to initiate early termination of the study.

At the end of the study, protocol deviations will be categorized as minor or major and their consequence on analysis populations will be decided.

18. Device Accountability

Each device prepared for the clinical study will get a unique serial number that will be marked on the device and on the box of the device. The devices will be brought by sponsor representative for each of the fittings as the sponsor responsible also will assist with the fitting. The device serial number will

be noted in the eCRF at the fitting visit. The sponsor will also keep a log of the device number and subject number. If any SPs are exchanged during the study the new number will be noted down together with date of exchanging the SP.

19. Statements of compliance

The clinical investigation will not be commenced until approval from both applicable regulatory authority and ethical committee has been received.

Ethical conduct of the investigation

The clinical investigation will be performed in consistency with the current version of the Declaration of Helsinki (Washington 2002), ISO 14155-2011 and applicable regulatory requirements and any additional requirements imposed by the EC.

Regulatory authorities

The clinical study will be submitted to and approved, in writing, by the Swedish regulatory authorities (MPA) prior to commencing the study. Any substantial changes to the investigational plan will be submitted for review. In case of any serious adverse events (SAE) the regulatory authority will be informed.

Ethics review

The investigation plan, including the final version of the patient Information and Consent Form must be approved in writing by an Independent Ethics Committee (IEC) before enrolment of any subject into the investigation. Substantial amendments to the Clinical Investigation Plan must be approved by the IEC if they influence the risk for the subject. Non-substantial amendments will be notified to the ethics committee.

Insurance

The subjects are covered by The Swedish Pharmaceutical Insurance and the Patient Injury Act. In addition the subjects are covered by insurance from the sponsor covering the use of the Fusion sound processor. This insurance covers use of the Fusion sound processor both during enrolment in this study but also use after study completion.

20. Informed consent process

The clinical investigator will ensure that the subject is given full and adequate oral and written information about the nature, purpose, possible risks and benefits involved. In this study this will be given over the telephone but also in written sent home to the subject. Subject will be notified that they are free to discontinue participation in the investigation at any time. The subject will be given time for consideration and the opportunity to ask questions before signing the informed consent form. This can be done by the subject contacting the investigator prior to the study or time will also be set aside on the first visit as the first thing on the visit. The subject signed informed consent must be obtained before conducting any procedures specifically for the investigation.

If any new information becomes available during the course of the trial that could influence the subjects' willingness to participate, the subject will be informed and asked to sign a revised informed consent.

The subject will consent in writing that the results obtained in the investigation may be used in authority assessment or submissions for publications in scientific journals with the condition that privacy and confidentiality is preserved. Subject will also consent in writing that concerned

personnel, sponsor representatives and concerned authorities may have access to the subject's medical record to perform source data verification.

The signed original of the consent form must be filed by the clinical investigator. A copy of the patient Information including the signed consent form should be given to the subject.

21. Adverse events, adverse device effects and device deficiencies

Any adverse events or serious adverse events, as described in Sec. 21.1 and Sec. 21.2, will be reported in this study as well as the parallel Osseofon study [REDACTED]. Any ongoing (S)AE at the conclusion of this study will be resolved in the Osseofon study. Any new AE's or SAE's that occur after the conclusion of this study but within the frame of the Osseofon study will be reported in the Osseofon study. An agreement to share relevant safety reporting data has been reached between the sponsors of the two studies to ensure adequate safety follow-up of the device.

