10.3. Investigation outline

Screening

The subjects will be contacted by phone by the sub-investigator who is well-known to the patients. The subject will be thoroughly informed about the study purpose and content including all study related visits. If the subject initially on the phone shows interest in participating in the study, informed consent together with written information will be sent to the patient and a first visit will be booked with the investigator.

First visit:

- Go through patient information and sign informed consent
- Patient's demographical data is registered in the electronic Case Report Form
- Skin evaluation

At the first visit the patient information will be gone through together with the subject and the patient will have the possibility to ask questions on the study and study procedures. If the subject wishes to participate in the study, the informed consent is signed. The investigator will then perform a base line skin evaluation.

Second visit, Fitting:

- Fill out the questionnaire for BCI SP
- Perform conventional BC-threshold measurements through audiometer and BC71 vibrator.
- Fitting of the Fusion sound processor including BC-insitu and feedback manager.
- Skull simulator measurements on the Fusion SP and BCI SP
- Sound field thresholds and speech intelligibility measurements on the BCI SP and Fusion SP
- Magnet force measurement
- Photo of the sound processor on the head
- Hand out of questionnaires for evaluation of Fusion SP
- [REDACTED]

The subject will start by filling out the questionnaire to evaluate the BCI SP. After that the fitting of the Fusion SP will be performed, a part of the fitting is to measure BC-insitu and feedback manager. As a reference for the BC- insitu thresholds conventional audiometric BC thresholds will also be measured at the second visit. The subjects' initial opinion about the sound will indicate if there is a need for fine tuning or not. The subject will be given the possibility to walk around with the SP in place and evaluate the sound.

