Sound field thresholds and speech intelligibility measurements will be performed both on Fusion SP and on BCI SP and photos will be taken with the sound processor on the head. To check the retention force of the magnet a magnet force measurement will be performed together with an evaluation of magnet strength and potential shift of magnet to a stronger or weaker if deemed necessary by the sub-investigator. At last questionnaires used for Fusion SP evaluation will be handed out.

[REDACTED]

If convenient for the subject, visit 1 and visit 2 can be carried out at the same day.

Phone call and potential extra visit

- Adverse events during the test period
- Evaluate need for fine tuning and conduct fine tuning
- Skull simulator on Fusion SP after fine tuning
- [REDACTED]

After approximately one week of usage the test subjects will be contacted by phone and interviewed about the usage of the Fusion SP. The purpose with the phone call is to in an early stage address potential issues using the Fusion SP as the setting potentially could differ somewhat compared to what the test subjects have been used to. If deviations are judged to be severe and affect the usage of the SP the test subject will be offered to come in for an additional fine tuning. At the extra visit fine tuning of the Fusion SP will be performed. The fine tuning will be verified through skull simulator measurements.

Third visit, one month after fitting:

- Adverse events during the test period

- Hand in questionnaire and interview about sound processor
- Magnet force measurement and skin evaluation
- Fine tuning if needed
- If fine tuning: skull simulator measurement with Fusion SP after fine tuning
- Sound field thresholds and speech intelligibility measurements Fusion SP and unaided
- Photo of the area under the sound processor.
- Hand out of questionnaires for evaluation of Fusion SP
- [REDACTED]

At the third visit after one month the test subjects hand in questionnaires on Fusion SP and magnet forces are measured again. Sound field thresholds and speech intelligibility measurements on Fusion will be performed. A photo of the area under the SP will be taken to help with evaluation of skin condition. If needed fine tuning will be performed with skull simulator measurement after. In the beginning of the visit eventual adverse events during the test period will be noted.

Fourth visit, six months

- Adverse events during the test period
- Hand in questionnaires

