10.5.1. Sample size calculation

The sample size calculation is based on the primary end-point. With Wilcoxon Rank test (compare Sec. 15. Statistical considerations) we need a minimum of 6 patients to reach statistical significance if all show improvements. Results from the BCI study on 6 patients [21] and studies on Bonebridge (another transcutaneous system with similar intended use and population, please refer to Sec. 5) show an average difference between aided and unaided free-field thresholds of 31dB (Sec. 5). Based on knowledge in the field and the primary end-point of this study, the minimum sample size is therefore 6 patients.

This sample size, although limited, will also provide valuable data on more general performance and satisfaction with the device, as described in the secondary objectives of the study. We therefore conclude that the minimum of six included patients is an adequate sample size.

11. Study Procedures

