11.3.4. Skin assement evaluation

Used for skin assessment is the recently developed IPS scale consisting of three parts: I (Infection/Irritation-scale) ranging from 0-4, P (Pain-Scale) ranging from 0-2 and S (Skin height/numbness-scale) ranging from 0-2. A higher score on either of the subscales reflects a more severe complication [20].

12. Monitoring plan

During the investigation, representatives from Oticon Medical will have regular contact with the investigation site. According to Good Clinical Practice (GCP) guidelines, the main task of the clinical trial monitor is to oversee the progress of a clinical study and to ensure that:

- The rights and well-being of human subjects are protected
- Reported trial data are accurate, complete and verifiable from source documents
- The conduct of the trial is in compliance with the currently approved protocol, SOPs, GCP and applicable regulatory requirements

Authorized representatives of the sponsor will therefore visit the centre to perform inspections as well as monitor the data captured in the electronic data system throughout the study.

13. Investigation administrative structure

[REDACTED]

[REDACTED]

[REDACTED]

[REDACTED]

[REDACTED]

[REDACTED]

[REDACTED]

[REDACTED]

[REDACTED]

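### Is the Sign test the wrong analysis for the IPS skin subscales when only 6 to 10 subjects are expected?

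*Combined protocol and SAP*

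**What the plan says.** Section 15 names the Wilcoxon signed rank test for the primary endpoint (unaided against Fusion-aided thresholds at six months). It then gives a general rule for other paired differences: signed rank for continuous variables, and "for ordered categorical variables with Sign test". No outcome is named under that rule, and alpha and sidedness are not given. Section 15 leaves the detail to a SAP that an independent biostatistician is to write before database lock.

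Section 11.3.4 describes the skin scale: "I (Infection/Irritation-scale) ranging from 0-4, P (Pain-Scale) ranging from 0-2 and S (Skin height/numbness-scale) ranging from 0-2". Skin is scored at the first visit (Section 10.3: "The investigator will then perform a base line skin evaluation"). It is scored again at one and six months, where the visit lists both carry "Magnet force measurement and skin evaluation". A paired change in IPS is therefore available and would fall under the Sign-test rule by default.

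On size, Section 10.5 says: "We expect between 6-10 of the subjects offered to participate will accept and be enrolled". Section 10.5.1 rests the minimum on the primary endpoint alone: "we need a minimum of 6 patients to reach statistical significance if all show improvements". It calls the sample limited and says only that it will also yield useful data for the secondary objectives.

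**The concern.** The argument in Section 10.5.1 works for thresholds because an average gain of 31 dB is expected, so all subjects may plausibly improve. Nothing similar is expected of a skin score with three or five levels, where many subjects may simply stay the same. The Sign test discards those subjects. With six enrolled, one unchanged subject is enough to put significance at two-sided 0.05 out of reach.

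Evaluating skin problems is a stated aim of the study (Synopsis and Section 4), and Section 23 allows the results to support an assessment by authorities. If the only named analysis can hardly ever be significant, a real worsening could be reported as non-significant and taken as reassurance. Counts with exact intervals would then look like the analysis the plan ought to have named.

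**Working it through.** **Inputs.** n = 6 to 10 (Section 10.5). No dropout: "we therefore expect all the subjects to fulfil the study and that there is no drop outs" (Section 10.5). Subscale ranges from Section 11.3.4. Alpha is not stated, so two-sided 0.05 is assumed. The rates of worsening below are also assumed, because the documents give none.

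**Step 1: the plan's own figure.** If all m non-zero differences point the same way, the smallest exact two-sided p is 2 × 0.5^m, for both the Sign test and the signed rank test.
- m = 5: 2/32 = 0.0625
- m = 6: 2/64 = 0.031

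The minimum of 6 in Section 10.5.1 is reproduced, which supports two-sided 0.05 as the working level. One-sided 0.05 would give a minimum of 5 (1/32 = 0.031).

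**Step 2: what the Sign test needs.** At least 6 changed subjects, which is 6/6 = 100% at n = 6, 6/8 = 75% at n = 8 and 6/10 = 60% at n = 10. With 6, 7 or 8 changed, all must move the same way:
- 6 of 7: 2 × (7 + 1)/128 = 0.125
- 7 of 8: 2 × (8 + 1)/256 = 0.070
- 8 of 9: 2 × (9 + 1)/512 = 0.039, the first case that allows one opposite change

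**Step 3: chance of significance.** If a share q worsens and nobody improves, the chance is P(Binomial(n, q) ≥ 6).

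| q (assumed) | n = 6 | n = 8 | n = 10 |
|---|---|---|---|
| 0.3 | 0.1% | 1.1% | 4.7% |
| 0.5 | 1.6% | 14% | 38% |
| 0.7 | 12% | 55% | 85% |

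The test is weak near n = 6 and at low to moderate rates. It is not weak at n = 10 with a high rate and no improvers.

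**Step 4: is this a fault of the test chosen?** By Step 1 the signed rank test on five non-zero pairs also stops at 0.0625. The limit comes from the number of informative pairs, so changing the test would not remove it.

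**Step 5: would the exact interval do the same job better?** The Clopper-Pearson upper limit for zero events is 1 − 0.025^(1/n): 45.9% at n = 6, 36.9% at n = 8 and 30.8% at n = 10. For 5 of 10 worsening the interval is 18.7% to 81.3%. It is the same whether the other five are unchanged (Sign test p = 0.0625) or all improved (5 against 5, p = 1). With 1 of 10 worsening it is 0.3% to 44.5%, so its lower limit is above zero as soon as one subject worsens. The interval estimates how often scores worsen. The Sign test asks whether worsening outweighs improvement. Subjects enter as users of another sound processor on the same implant (Section 10.4.1), so change in either direction is possible and the two questions differ.

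**Step 6: what the plan claims.** Section 10.5.1 sizes the study on the primary endpoint only. Section 15 states its rule in general terms, gives secondary p-values no confirmatory role and does not rule out descriptive summaries. It names no estimate or interval for the primary endpoint either, so their absence for IPS reflects a summary-level section and not a special gap for skin.

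**The case for a change.** The best case for the concern is practical. Section 15 names a test and nothing else for these outcomes, and skin is a stated aim. Five of ten subjects worsening with none improving would come out at p = 0.0625, which a careless reader could take as no effect. The SAP is still to be written, so asking for counts and intervals costs little.

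The arithmetic stands, and so does the caution that a non-significant result at this size says little. The step to a defect does not follow. No available passage proposes to infer absence of a skin effect from non-significance. Counts of better, same and worse, the alpha level and the handling of ties are ordinary SAP content, and the protocol expressly leaves detail to the SAP. Skin findings also do not depend on this p-value: photographs (Section 11.3.1.1) and adverse events (Section 21) are recorded as well.

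The text of Sections 9, 10.1 and 10.2, on objectives, endpoints and outcome measures, is not in the public copy. Whether IPS is a tested or a purely descriptive outcome therefore cannot be established, and silence in Section 15 cannot be counted against the plan.

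**Conclusion.** The concern does not hold. The Sign test is a valid choice for paired ordinal data, and followed as written the plan gives no wrong result. What the calculation shows is low power on a non-primary outcome for which no power is claimed: from 0.1% to 85% over assumed worsening rates of 30% to 70% and n = 6 to 10, if nobody improves. Any paired test of direction meets the same floor of 0.0625 with five informative pairs. Adding exact intervals would be a reporting preference. They are wide and answer a different question.

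This conclusion assumes two-sided 0.05, which the plan's own minimum of 6 supports. Under one-sided 0.05 the threshold falls from 6 to 5 changed subjects and the conclusion is the same. It also assumes that neither the unavailable sections nor the later SAP treats a non-significant Sign test as proof of no skin effect. The primary endpoint, the sample size and the data collected are not affected.
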